### **B. Primary Efficacy Endpoint Analysis**

The primary analysis will use a mixed effect repeated measures model on the log-transformed data to assess differences between treatments using the FAS. A

random subject-level effect will be used to accommodate dependence in responses within subjects over time. Fixed main effect terms for period, treatment, treatment\*period interaction and baseline normalized Hb AUC will be included in the model. Mirasol-treated WB will be coded as 1 and conventional treatment will be coded as 0 in the model.

A one-sided 97.5% confidence interval for treatment differences will be used to test the primary hypothesis that the normalized Hb AUC as a measure of RBC survival derived from Mirasol-treated WB is non-inferior to normalized Hb AUC after transfusion of conventional untreated RBCs. Assuming a non-inferiority margin of 20% (at the original scale), the use of RBCs derived from Mirasol-treated WB will be declared non-inferior to conventional, untreated RBCs if the lower limit of the one-sided confidence interval for the treatment effect (RBCs derived from Mirasol-treated WB mean minus conventional) is greater than  $\ln(0.80) = -0.2231$ .

The following provides sample code for implementing the MMRM analysis:

```
ods output lsmeans=lsmeans diff=diffs;
proc mixed data=test;
class subjid trt period trannum;
model resp=period trt trt*period trannum basehb/ddfm=kr;
random subjid(sequence)/sub=subjid type=cs;
lsmeans trt/diff alpha=.05;
```

where

- RESP is the log(normalized Hb AUC)
- TRT is the variable for treatment (0 for REF RBCs; 1 for MIR RBCs)
- BASEHB is the pre-treatment Hb
- PERIOD is the variable for period
- TRANNUM is the variable to identify the order of the two transfusions following the 50-day washin-in period for each treatment period (1 for first transfusion, 2 for second transfusion)
- SUBJID is for subject

The carryover effect will be tested with the TRT\*PERIOD interaction term. If the interaction is significant, then a carryover effect may be present and alternative analysis methods may be considered.

Several secondary/exploratory analyses will be conducted on the primary endpoint. Each are described below:

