Safety Assessments:	
Safety will be evaluated by assessment of physical examinations, vital signs, clinical laboratory values, TEAEs, UADEs, SAEs, and discontinuations due to treatment-related AEs. Safety will be assessed according to the National Cancer Institute (NCI) Common Toxicity Criteria for Adverse Events (CTCAE) scale, Version 4.03.
 
This trial will be monitored using an independent Data Monitoring Committee (DMC) operating under a ratified charter. The DMC will review SAE/UADE reports on an ongoing basis. Additionally, the DMC will review safety reports summarizing the frequency and severity of TEAEs, UADEs, and other relevant safety information as defined in the DMC charter. Enrollment will not be placed on hold during the DMC review process. The DMC will determine if the observed AEs are acceptable for this patient population, and will make recommendations to the Sponsor regarding study continuation.

Statistical Methodology:	
Eligible subjects will be randomized to treatment sequence via an electronic system using a permuted-block schedule stratified by investigational site. The primary endpoint will be the normalized Hb AUC calculated from normalized Hb between successive transfusions as a measure of the percent surviving RBCs and will be evaluated for the first 2 transfusions after a 50-day wash-in for each treatment period. These 2 measurements of normalized Hb AUC within each period will be used for analysis.
 
The primary hypothesis is that the normalized Hb AUC as a measure of RBC survival derived from Mirasol-treated WB is not inferior to normalized Hb AUC after transfusion of conventional untreated RBCs. The study has approximately 80% power to show the decrease in normalized Hb AUC of RBCs derived from Mirasol-treated WB is not more than 20% of the decrease in normalized Hb AUC of conventional untreated RBCs, assuming a 1-tailed type 1 error rate of 2.5%.

TABLE OF CONTENTS

1	INTRODUCTION.....	18
1.1	Pathogen Risk	19
1.2	White Blood Cell Risk.....	21
1.3	Novel Device	22
2	DEVICE DESCRIPTION	22
2.1	Device Description.....	22
2.2	Principles of Operation	23
2.3	Principles of Use	23
3	INTENDED USE STATEMENT.....	24
4	NONCLINICAL STUDIES.....	24
5	CLINICAL TRIAL EXPERIENCE.....	25
5.1	The IMPROVE Study	25
5.2	The IMPROVE II Study	26
5.3	The AIMS Study	27
6	RATIONALE FOR THE CURRENT STUDY	28
7	OBJECTIVES	29
7.1	Primary Objective	29
7.2	Secondary Objective	29
8	EFFICACY ENDPOINTS.....	29
8.1	Primary Endpoint	29

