21.7.1 Endpoint Measures

21.7.1.1 Primary Endpoint

The primary endpoint is normalized Hb AUC as a measure of the percent surviving RBCs. The Hb AUC is calculated using the trapezoidal method on normalized Hb. The normalization is accomplished by dividing all posttransfusion Hb values by the 15-minute posttransfusion Hb level. The ratio is expressed as a percentage. A natural log-transform of the observed normalized Hb AUC will be utilized.

The Hb will be collected within 1 hour before transfusion, 15 (+ 5) minutes, 24 ± 6 hours, and 7 days after transfusion and at the end of study treatment follow-up. The transformed Hb AUC values from the first 2 transfusion episodes after the 50 day wash-in for each period will be used for analysis. If only a single Hb AUC value is available after the wash-in for an individual period, that single value will be used for analysis.

If a patient randomized to receive RBCs derived from Mirasol-treated WB in a particular period receives 2 successive off-protocol transfusions (ie, untreated RBCs) after completing the 50 day wash-in period, the primary endpoint for that period will be excluded from the analysis. If only 1 of the 2 successive transfusions after the 50 day wash-in period is per protocol, only the primary endpoint associated with the per protocol transfusion will be analyzed.

The primary analysis will use a mixed effect repeated measures model on the log-transformed data to assess differences between treatments using the FAS. A random subject-level effect will be used to accommodate dependence in responses within subjects over time. Fixed main effect terms for period and carry-over will be modeled along with treatment, where Mirasol-treated WB is coded 1 and conventional treatment is 0. A one-sided 97.5% confidence interval for treatment differences will be used to test the primary hypothesis that the normalized Hb AUC as a measure of RBC survival derived from Mirasol-treated WB is non-inferior to normalized Hb AUC after transfusion of conventional untreated RBCs. Assuming a non-inferiority margin of 20% (at the original scale), the use of RBCs derived from Mirasol-treated WB will be declared non-inferior to conventional, untreated RBCs if the lower limit of the one-sided confidence interval for the treatment effect (RBCs derived from Mirasol-treated WB mean minus conventional) is greater than $\ln(0.80) = -0.2231$.

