## C. Sample Size Estimation

Data from the IMPROVE II study were available to obtain information on normalized Hb AUC associated with RBCs derived from Mirasol-treated WB as well as from untreated WB. Pairwise differences in the natural log-transform of normalized Hb AUC from treatment and control were used to obtain estimates required for determining the sample size needed for this study.

The mean difference in log-transformed Hb AUC values suggests a reduction of 16.7% resulting from the use of MIR RBCs. The sample variance of within subject differences is 0.015412. The estimate of the within subject variance required for the 2x2 crossover design is one-half of the variance of within subject differences (0.007706).

The primary hypothesis is that RBCs derived from Mirasol-treated WB are not inferior to conventional, untreated RBCs with respect to normalized Hb AUC. Assuming a within subject variance of 0.007706 and a 16.7% reduction in normalized Hb AUC, approximately 77 subjects are needed to obtain at least 80% power to show the decrease in normalized Hb AUC from RBCs derived from Mirasol-treated WB is not more than 20% of the normalized Hb AUC from conventional untreated RBCs assuming a 1 tailed type 1 error rate of 2.5%. Algebraically if  $\ln(\mu_M)$  is the mean of the natural log-transformed Hb AUC for MIR RBCs and  $\ln(\mu_C)$  is the mean of the natural log-transformed Hb AUC for REF RBCs, the sample size is calculated to detect an alternative hypothesis versus a null hypothesis stated as:

$$H_0 : \ln(\mu_M) - \ln(\mu_C) \leq -22.3\% \text{ versus } H_a : \ln(\mu_M) - \ln(\mu_C) > -22.3\%$$

In the original scale (indicated by \*), the above hypotheses translate to:

$$H_0 : \frac{\mu_M^*}{\mu_C^*} \leq 0.80 \text{ versus } H_a : \frac{\mu_M^*}{\mu_C^*} > 0.80$$

Assuming a potential 20% discontinuation rate, approximately 97 patients may be enrolled.

The sample size was calculated using SAS 9.3 proc power for paired two samples t-test with option for finding difference with the null difference at the non-inferiority margin of -0.2231 (corresponding to 20% non-inferiority margin at the original scale), true mean of -0.1839 (corresponding to 16.7% observed

decrease in IMPROVE II), and correlation of 0.35. Should the correlation be higher, the proposed sample size will have higher power for the non-inferiority test.

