### **D. Covariate Adjustment in Primary Analysis**

Pre-transfusion Hb level will be included as a covariate in the primary analysis.

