### **A. Efficacy Outcomes**

#### **Primary Endpoint**

The primary endpoint is normalized Hb AUC as a measure of the percent surviving RBCs. The normalized Hb AUC is calculated using the trapezoidal method on normalized Hb. The normalization is accomplished by dividing all post-transfusion Hb values by the 15-minute post-transfusion Hb level. The ratio is expressed as a percentage. A natural log-transform of the observed normalized Hb AUC will be utilized.

The normalized Hb AUC is expected to be calculated using four timepoints: the 15-minute post transfusion, 24-hour, Day 7, and end of transfusion interval (ie, pre-transfusion measure for the subsequent interval). If either the 24-hour or Day 7 measure is missing, the AUC will still be calculated using the following rule. If both are missing, or if either the 15-minute post transfusion or the end of transfusion interval are missing, then no AUC will be calculated for that interval.

A single value imputation approach will be used to estimate the missing percent decrease at either the 24 hour or Day 7 (but not both). The median of the observed normalized Hb levels (ie, percent decreases) for the treatment received at that particular time point and transfusion interval number will be used so that the AUC is based on 4 values of normalized Hb. This approach takes advantage of all the observed data rather than assuming an entire AUC is missing in the presence of a single missing Hb value.

The approximations are conservative in the sense that they bias towards inferiority in the case of missing Hb values for the normalized Hb AUC calculation.

The Hb will be collected within 1 hour before transfusion, 15 (+ 5) minutes, 24 ( $\pm$  6) hours, and 7 ( $\pm$  1) days after transfusion and at the end of study treatment follow-up. The transformed normalized Hb AUC values from the first 2 transfusion episodes after the 50-day wash-in for each period will be used to obtain a single measure associated with each treatment. If only a single

normalized Hb AUC value is available after the wash-in for an individual period, that single value will be used for analysis.

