### **Imputation of Missing Values Analysis**

As a sensitivity analysis, missing normalized Hb AUC values will be imputed. In this analysis, any missing normalized Hb AUCs will be imputed using the SAS procedure for Multiple Imputation (Proc MI).

- 1) The pattern of missingness will be analyzed and determined to be either monotone or arbitrary.
- 2) If the missingness pattern is arbitrary, then the MCMC method will be used to impute just enough missing values to make the imputed data sets have monotone missing patterns.
- 3) PROC MI will then be used to impute the remainder of the missing data (in a monotone pattern) using linear regression.
- 4) MMRM model will be used to produce point estimates and associated standard errors for the treatment difference.
- 5) PROC MIANALYZE will be used to combine the collection of point estimates and SEs and create a 95% CI to make inferences.

The variables used in the MI process will be (pooled) treatment, age, gender, normalized Hb AUC from transfusion episodes during the wash-in period, pre-transfusion Hb level, and normalized Hb AUC from previous transfusion in the same treatment/control period. The number of imputations used in the MI process will be 100.

The primary endpoint in each imputation dataset will then be analyzed similarly to the primary analysis of the primary endpoint described above. The point estimates and associated SEs of the treatment difference for each imputation dataset will be analyzed using PROC MIANALYZE. The result will be summarized as the MI estimate of the treatment difference and associated 95% confidence interval.

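### The primary model enters two AUCs per period with only a subject effect, so the standard error behind the non-inferiority limit is too small if same-period AUCs correlate more than different-period AUCs

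*SAP*

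**What the plan says.** SAP VIII.A (Primary Endpoint) says that the log AUCs from the first two transfusion episodes after wash-in "will be used to obtain a single measure associated with each treatment". It does not say how.

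SAP VIII.B (Primary Efficacy Endpoint Analysis) models each AUC as its own record. In its definitions, "TRANNUM is the variable to identify the order of the two transfusions following the 50-day washin-in period for each treatment period", and that variable is in both the CLASS and MODEL statements. The only covariance statement is "random subjid(sequence)/sub=subjid type=cs". There is no REPEATED statement and no subject-by-period term. The prose agrees with the code in specifying a single subject-level random effect.

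The protocol also analyses both values. Its synopsis says "These 2 measurements of normalized Hb AUC within each period will be used for analysis", and Section 21.7.1.1 says "A random subject-level effect will be used to accommodate dependence in responses within subjects over time". So on the number of records, SAP VIII.A is the outlier.

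The sample size (SAP IV.C) comes from "SAS 9.3 proc power for paired two samples t-test", that is, one paired difference per subject. On covariates, SAP VI.D says "Pre-transfusion Hb level will be included as a covariate in the primary analysis".

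**The concern.** In this 2x2 crossover each subject contributes four AUCs, two per period, and both AUCs of a period are on the same product. The treatment difference is therefore a between-period contrast within subjects. Anything specific to a subject in one period, including a patient-specific response to one product, moves both AUCs of that period together and does not average out over the two transfusions.

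A model with only a subject effect has no place for this component. It pools the variation between the two transfusions of a period with the variation between periods, and uses the pooled figure as the error for treatment. If subject-by-period variance is positive, the standard error is too small.

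That standard error sets the lower 97.5% limit that is compared with ln(0.80), the only rule for declaring non-inferiority. A limit that is too favourable raises the chance of declaring non-inferiority for a product that sits at the margin.

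**Working it through.** **Inputs (SAP IV.C).** Variance of within-subject differences 0.015412; within-subject variance W = 0.007706; between-period correlation 0.35; margin -0.2231; assumed true difference -0.1839; one-sided 2.5%; 77 evaluable subjects, 97 randomized.

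**The plan's own figure.** A paired t-test with SD = sqrt(0.015412) = 0.1241 and true difference ln(0.833) = -0.1827 gives n = 77 with power 80.5%. The printed -0.1839 gives 78.1% at n = 77 and would need n = 81. With 20% dropout, 77/0.80 rounds up to 97. So the planned size is reproduced, on the basis of one value per treatment.

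**Variance components.** Let f be the share of W that the two AUCs of one period have in common. f is an assumption; the documents do not give it. Then:

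- subject-by-period variance = fW and residual variance = (1-f)W;
- different-period correlation = 0.35, and same-period correlation = 0.35 + 0.65f.

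**True variance of the treatment difference.** The difference between a subject's two period means has variance 2fW + (1-f)W = W(1+f). Over n subjects in two equal sequences, Var = W(1+f)/n.

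**Variance the coded model reports.** Each subject supplies one between-period contrast, with mean square W(1+f), and two within-period contrasts, each with mean square W(1-f). Pooling them gives W[(1+f) + 2(1-f)]/3 = W(1-f/3), so the reported variance is W(1-f/3)/n, on 3n-3 df. The exact pooling weights, n-2 and 2n-1, were used for the error rates.

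**Ratio.** True SE / reported SE = sqrt[(1+f)/(1-f/3)]. At f = 0.25 this is sqrt(1.25/0.9167) = 1.17; at f = 0.5 it is sqrt(1.5/0.8333) = 1.34.

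**Results, n = 77, complete data, no covariate.** The last column is the power of the corrected analysis (n-2 df) at a true difference of -0.1839.

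| f | Same-period correlation | Reported SE | True SE | One-sided error, coded model | Power, corrected |
|---|---|---|---|---|---|
| -0.1 | 0.29 | 0.0102 | 0.0095 | 1.8% | 98% |
| 0 | 0.35 | 0.0100 | 0.0100 | 2.5% | 97% |
| 0.05 | 0.38 | 0.0099 | 0.0102 | 2.9% | 97% |
| 0.1 | 0.42 | 0.0098 | 0.0105 | 3.3% | 96% |
| 0.25 | 0.51 | 0.0096 | 0.0112 | 4.7% | 93% |
| 0.5 | 0.68 | 0.0091 | 0.0122 | 7.2% | 88% |
| 0.75 | 0.84 | 0.0087 | 0.0132 | 10% | 83% |

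**Checks by simulation.** With 20,000 runs per value of f (78 subjects, true difference at the margin), the coded model's error was 2.5%, 3.5%, 4.5%, 7.5% and 9.9% at f = 0, 0.1, 0.25, 0.5 and 0.75. One mean per period gave 2.3% to 2.7% throughout. REML random-intercept fits of the coded fixed effects (76 subjects, 6,000 runs per setting) gave 2.8%, 5.2% and 7.8% at f = 0, 0.25 and 0.5 without a covariate.

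**Effect of the baseline covariate.** One value per subject does not change the result. If it is period-specific and explains a share r2 of the subject-by-period variance, f becomes f(1-r2)/(1-f·r2). At f = 0.25 the error is 4.2% for r2 = 0.25 and 3.7% for r2 = 0.5. At f = 0.5 it is 6.5% and 5.5%. The r2 values are assumed.

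**What does not repair it.** Kenward-Roger degrees of freedom do not restore a variance component that was never fitted. With `sub=subjid`, `type=cs` on a single subject effect adds no period-level correlation. The treatment-by-period term is the sequence contrast in a 2x2 design and absorbs no subject-by-period variance.

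**The case against.** **The size and sign of f are unknown.** This stands. At f = 0 the coded model is valid, at small f the inflation is slight (2.9% at 0.05), and at negative f the test is conservative.

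**The documents offer little direct evidence that f is positive.** This stands in part. The imputation model uses "normalized Hb AUC from previous transfusion in the same treatment/control period", but ordinary within-subject correlation would justify that too. The better grounds are in the design. The two AUCs are consecutive intervals on one product, and a patient-specific response to a product is shared by both. Reference units may also differ in irradiation, age and storage solution, which the SAP itself plans to examine; if these repeat within a patient, both reference AUCs share them. This makes a positive f plausible, not established.

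**The SAP VIII.A clause is loose and names no model.** Fair: the clause sets no averaging rule or standard error, and at f = 0 both approaches have the same expected standard error. The covariance gap does not depend on that clause, because the prose and code of VIII.B share it.

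**Sizing on one value and analysing two is conservative.** True for sample size. It does not protect the type I error of the coded test.

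**The SAP requires a covariate, and the main figures omit it.** Baseline is defined per treatment period (SAP VI.A), so a period-specific reading is reasonable. However, the prose of VIII.B names baseline normalized AUC while the code defines pre-treatment hemoglobin. How much either would absorb is unknown.

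**The verdict would rarely change.** At an estimate of -0.1839 and f = 0.5, the limits are -0.1839 - 0.0180 = -0.202 and -0.1839 - 0.0244 = -0.208, and both clear -0.2231. The conclusion differs only for estimates in a band about 0.006 wide (0.003 at f = 0.25). That is useful context, but error control is judged at the margin, and the assumed effect lies only 0.039 from it.

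**Conclusion.** The concern holds as a conditional statement. SAP VIII.A and VIII.B disagree on whether one or two values per period are analysed, and the VIII.B model leaves out part of any positive subject-by-period variance. If same-period and different-period AUCs correlate equally, nothing is lost. If the same-period correlation is 0.51 rather than 0.35, the one-sided error is 4.7%; at 0.68 it is 7.2%. These figures assume 77 subjects, complete balanced data and no covariate; a period-specific covariate lowers them by an unknown amount. With complete balanced data and no period-specific covariate, the point estimate is the same either way, and only the standard error and degrees of freedom change.

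This should be corrected before database lock. The only confirmatory test should not rest on an unstated equal-correlation assumption whose plausible failure favours the non-inferiority claim.

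**What to change.** State one rule in SAP VIII.A and VIII.B. Either:

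- average the two log AUCs within each subject and period and fit one value per period; or
- keep both records and add a subject-by-period random effect, for example `random subjid subjid*period;`. This also handles periods with a single AUC.

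State that the per-protocol and multiple-imputation analyses of the primary endpoint use the same structure. Correct the code, where `sequence` appears in RANDOM but is not in CLASS or among the defined variables.

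**Cost.** One line of text and code, and no added patients. If f is positive, the SE is wider than under the coded model, by about 17% at f = 0.25 and 34% at f = 0.5. The corrected variance, 0.007706(1+f)/n, cannot exceed the 0.015412/n used for the sample size, because f is at most 1. With 77 subjects and a true difference of -0.1839, power is 93% at f = 0.25, 88% at f = 0.5 and 80% at f = 0.9. At the limit f = 1 it is 78%, the same as the planned paired test at that difference.

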### **Per Protocol Analysis**

As a secondary analysis, the primary endpoint will be analyzed as described above using the PPS.

### **Imputation of Missing Values Analysis**

As a sensitivity analysis, missing normalized Hb AUC values will be imputed. In this analysis, any missing normalized Hb AUCs will be imputed using the SAS procedure for Multiple Imputation (Proc MI).

- 1) The pattern of missingness will be analyzed and determined to be either monotone or arbitrary.
- 2) If the missingness pattern is arbitrary, then the MCMC method will be used to impute just enough missing values to make the imputed data sets have monotone missing patterns.
- 3) PROC MI will then be used to impute the remainder of the missing data (in a monotone pattern) using linear regression.
- 4) MMRM model will be used to produce point estimates and associated standard errors for the treatment difference.
- 5) PROC MIANALYZE will be used to combine the collection of point estimates and SEs and create a 95% CI to make inferences.

The variables used in the MI process will be (pooled) treatment, age, gender, normalized Hb AUC from transfusion episodes during the wash-in period, pre-transfusion Hb level, and normalized Hb AUC from previous transfusion in the same treatment/control period. The number of imputations used in the MI process will be 100.

The primary endpoint in each imputation dataset will then be analyzed similarly to the primary analysis of the primary endpoint described above. The point estimates and associated SEs of the treatment difference for each imputation dataset will be analyzed using PROC MIANALYZE. The result will be summarized as the MI estimate of the treatment difference and associated 95% confidence interval.

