The linear mixed-effect model accommodates incomplete data arising if some patients do not yield responses to two transfusions in each treatment period. Moreover as this model is likelihood based findings will be insensitive to missing at random mechanisms. In a tertiary analysis any missing AUCs will be imputed using the SAS procedure for Multiple Imputation (Proc MI). The variables used in the MI process will be (pooled) treatment, age, gender, normalized AUC from transfusion episodes during the wash-in period. The number of imputations will be n=10 and the treatment effect for each imputation dataset will be analyzed using Proc MIANALYZE. The result will be summarized as the MI estimate of the treatment effect, standard error, and a 95% confidence interval.

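### The multiple-imputation check omits period, sequence and the subject's other-period AUCs, and leaves pooled treatment undefined

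*SAP*

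**What the plan says.** The SAP (VIII.B, Imputation of Missing Values Analysis) imputes missing normalized Hb AUCs with PROC MI, fits the primary model to each completed data set and combines the results. The predictors are a closed list: "The variables used in the MI process will be (pooled) treatment, age, gender, normalized Hb AUC from transfusion episodes during the wash-in period", plus pre-transfusion Hb and the AUC of the previous transfusion in the same period. There are 100 imputations. Protocol 21.7.1.1 calls this a tertiary analysis, with a shorter list and 10 imputations: "The variables used in the MI process will be (pooled) treatment, age, gender, normalized AUC from transfusion episodes during the wash-in period".

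The model fitted to each completed data set is richer. SAP VIII.B gives it "Fixed main effect terms for period, treatment, treatment\*period interaction" and a baseline term, with a random subject effect; the sample code adds transfusion number.

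Neither document defines pooled, or says whether the imputation data set has one row per subject or one per transfusion episode. The primary analysis does not impute missing AUCs (SAP VIII).

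**The concern.** An imputation model should contain at least the structure of the analysis that follows it. In a two-period crossover, that structure is the pairing within subject, the period effect and the sequence (which is the same contrast as treatment by period). None of the three is in the list.

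The gap matters most for a subject who stops after Period 1. The full analysis set needs only one AUC, so that subject is analysed. No Period 2 wash-in AUC or previous same-period AUC exists, and the assessed Period 1 AUCs are not listed. The primary mixed model does use them. The check therefore discards outcome data that the analysis it is meant to test retains. Protocol 21.7 names early dropout as the reason for such analyses, and this is the only missing-data sensitivity analysis that the SAP specifies.

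The undefined word pooled adds a second problem: one possible reading removes the treatment contrast from the imputed values.

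**Working it through.** **Inputs** (SAP IV.C). Type 1 error: "assuming a 1 tailed type 1 error rate of 2.5"%. Sample size: "approximately 77 subjects are needed to obtain at least 80% power". Margin: "null difference at the non-inferiority margin of -0.2231". Effect: "true mean of -0.1839". Variance: "The sample variance of within subject differences is 0.015412". Correlation 0.35; discontinuation 20%. The documents give no rate or mechanism for missing Period 2 AUCs and no period effect, so those below are assumptions.

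**Step 1: the plan's own figure.** SD of differences = √0.015412 = 0.12415. A paired t-test against -0.2231 with a true difference of ln(0.833) = -0.1827 needs 76 subjects and has 80.5% power at 77. The printed -0.1839 needs 81 and has 78.2% power at 77. So 77 is reproduced to within one subject from the 16.7% reduction. 77/0.8 = 96.25, hence 97. The plan gives no figure for the imputation analysis.

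**Step 2: cost of ignoring the pairing.** Within-subject variance = 0.015412/2 = 0.007706. Total variance = 0.007706/(1 - 0.35) = 0.011855. A value drawn without regard to the subject's other value gives a pair difference with variance 2 × 0.011855 = 0.02371. With 20% of pairs imputed, the average is 0.8 × 0.015412 + 0.2 × 0.02371 = 0.01707. That is about 11% above 0.015412, or about 5% in standard error.

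**Step 3: simulation.** 77 subjects, 1:1, one AUC per period, Period 2 values removed, no covariates. Normal-regression imputation, 10 imputations, Rubin's rules, period-adjusted estimate, 400 replicates. Monte Carlo error is about 0.0008 on estimates and 1 to 2 points on probabilities. One-sided scenarios take all the loss from one sequence, so 20% of Period 2 is 40% of that sequence. Cells show the mean estimate and the probability of declaring non-inferiority. The true difference is -0.1839 in the first row and -0.2231 (the margin) elsewhere. MCAR means missing completely at random; MAR means missing depending on the observed Period 1 AUC.

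| Period 2 loss | Full data | Treatment only | Plus sequence/period and other-period AUC | Treatments merged |
|---|---|---|---|---|
| 20% MCAR, planned effect | -0.1839; 78.7% | -0.1836; 67.7% | -0.1836; 71.8% | -0.1655; 93.2% |
| 20% MCAR | -0.2220; 2.2% | -0.2214; 1.5% | -0.2214; 2.5% | -0.1993; 20.7% |
| 10% MCAR | -0.2222; 4.3% | -0.2222; 3.3% | -0.2221; 4.3% | -0.2111; 8.5% |
| 20% MAR, both sequences | -0.2245; 1.8% | -0.2241; 1.5% | -0.2244; 1.0% | -0.2013; 15.8% |
| 20% MAR, after low MIR | -0.2231; 1.8% | -0.2310; 0.0% | -0.2229; 2.2% | -0.2055; 11.7% |
| 20% MAR, after low REF | -0.2232; 1.5% | -0.2158; 4.5% | -0.2233; 1.5% | -0.1921; 32.3% |
| 20% MCAR after MIR only, period +0.05 | -0.2226; 2.5% | -0.2158; 4.8% | -0.2225; 3.3% | -0.1918; 34.5% |
| 20% MCAR after MIR only, period -0.05 | -0.2234; 2.2% | -0.2294; 1.0% | -0.2231; 2.2% | -0.2037; 11.3% |

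**Step 4: reading the table.**
- Treatment only: no bias under MCAR. In the first row the mean standard error is 0.0161, against 0.0155 with the added terms. The spread of the estimates is nearly equal (0.0151 and 0.0153), so the excess is mainly an overstated interval.
- Treatment only, one-sided loss: the shifts from full data are -0.0079, +0.0074, +0.0068 and -0.0060. With 10% missing, the two MAR estimates are -0.2261 and -0.2196, about half the shift.
- With the added terms, no shift from full data exceeds about 0.001.

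**Step 5: hand checks.**
- Period effect: with 40% of one sequence missing, imputed REF values carry 0.6/1.6 of the period effect. The shortfall is 0.05/1.6 = 0.03125, and the shift is 0.5 × 0.4 × 0.03125 = 0.00625, in line with the simulation.
- Merged treatments: 20% of pairs lose half the difference, so the estimate is (0.8 + 0.2/2) = 0.9 of the truth; 0.9 × -0.1839 = -0.1655, as simulated.

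**The case against.** The strongest reply is that treatment is itself on the predictor list. If the arms were merged there would be no treatment variable to list, and pooling over periods, sequences or sites is at least as natural a reading. A reader might infer that the imputation as specified drives the result toward non-inferiority. The documents do not support that. With treatment kept, MCAR loss gives no bias and a wider interval, which works against non-inferiority. One-sided loss shifts the estimate either way, and after poor MIR results it shifts away from non-inferiority. This part of the objection stands.

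Three further points stand in part.
- The list includes pre-transfusion Hb and the previous same-period AUC, which carry subject information when only the second episode is missing. Nor is the wash-in AUC restricted to the same period, so Period 1 wash-in AUCs might inform a Period 2 imputation, depending on a layout the SAP does not state. The simulation has none of these predictors and shows the dropout case at its barest.
- A reader might take the plan's 20% as the share of Period 2 AUCs missing. It is the allowance from 97 randomized to 77 in the full analysis set, which needs only one AUC. AUCs can also be lost through missed Hb samples or off-protocol episodes.
- The variance of an imputed pair difference is 54% larger (0.0237 against 0.0154), but this applies to imputed pairs only; Step 2 gives the effect on the whole analysis.

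The reply does not reach the omission itself. The list leaves out the assessed AUCs of the other period, and period and sequence, under every reading.

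**Conclusion.** The point holds as a weakness of the sensitivity analysis. The stated imputation model is poorer than the analysis model and, for a subject who stops after Period 1, ignores that subject's assessed Period 1 AUCs. With treatment as a predictor, and 20% of Period 2 assumed missing, the cost is a slightly larger reported standard error under MCAR (0.0161 against 0.0155) and a bias of about 0.007, of either sign, under one-sided MAR loss or one-sided loss with an ignored period effect of 0.05. For scale, the planned effect lies 0.2231 - 0.1839 = 0.0392 from the margin. Equal MAR loss in both sequences cancels.

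A systematic pull toward zero requires merged treatments. It would then be serious: false non-inferiority of 20.7% at the margin with 20% MCAR and 8.5% with 10%. The text does not say this; it only fails to exclude it.

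A reader might also infer that the trial's conclusion is at risk. It is not. The primary analysis imputes no missing AUC, and its likelihood-based model already uses both periods. What suffers is the value of this analysis as a check on it.

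**What to change.** In the SAP, replace the predictor list and the term pooled treatment with wording to this effect: *Missing AUCs will be imputed from one record per subject holding all assessed AUCs of both periods. The imputation model will include sequence, so that each period's actual treatment is kept and treatments are not merged; the subject's assessed AUCs from the other period; wash-in AUCs; the pre-transfusion Hb of each period; age; and sex.*

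In this layout the period is identified by the column and the treatment by sequence and column together. Placing Period 1 before Period 2 makes dropout after Period 1 a monotone pattern, which suits the regression step already planned. Period 2 predictors that are themselves missing should be imputed in the same run. The matching sentence in Protocol 21.7.1.1 can be aligned at the next amendment.

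Every variable is already collected, and neither the sample size nor the primary analysis changes. The cost is SAP wording, settled before database lock. The gain is a robustness check that respects the crossover and cannot be programmed in two ways.
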